#### Table 14.2.4.2

Difference in Mean Change for Sitting Systolic (SBP) and Diastolic Blood Pressure (DBP) from Visit 2 to Visit 3 for Patients with Uncontrolled BP at Visit 3 (Efficacy Population)

			S	BP	D	BP
		-	ZOF/AML [4]	ACE-i/CCB [5]	ZOF/AML [4]	ACE-i/CCB [5]
Visit [1]	Statistic Type [2,3]	Statistic	(N=xx)	(N=xx)	(N=xx)	(N=xx)
Visit 3 CFB	MMRM	n LSM (SE) 95% Cl	xx xx.x (xx.xxx) (xx.x, xx.x)	xx xx.x (xx.xxx) (xx.x, xx.x)	xx xx.x (xx.xxx) (xx.x, xx.x)	xx xx.x (xx.xxx) (xx.x, xx.x)
	v. ACE-i/CCB	LSM Difference (SE) 95% Cl p-value	xx xx.x (xx.xxx) x.xxx		xx xx.x (xx.xxx) x.xxx	

1] CFB = Change from Baseline (Visit 2).

[2] MMRM = Mixed Model Repeated Measures.

[3] Model uses an unstructured covariance matrix; change from baseline for SBP/DBP as the response variable; visit, treatment subgroup, visit\*treatment subgroup interaction, and baseline SBP/DBP as covariates; and a random effect for patient.

[4] ZOF/AML subgroup: Patients who were on ZOF 30 mg or AML 5 mg at Visit 1 (Week -4) and continued on same therapies.

[5] ACE-i/CCB subgroup: Patients who switched to ZOF 30 mg or AML 5 mg from any other ACE-I or CCBs at Visit 1 (Week -4).

Source: Listing 16.2.6

Program Name: XXXX.SAS

Date: DDMMMYYYY

Programming Note:

• If a different covariance structure is used in case of model nonconvergence, footnote 3 should be updated accordingly.

Table 14.2.4.3
Proportion of Patients Achieving Sitting BP Goal (≤ 130/80 mmHg) at Visits 2, 3, and 4 by Treatment Subgroup
(Full Analysis Set and Efficacy Population)

				ZOF/AML [5]	ACE-i/CCB [6]
Therapy Type	Visit	Statistic Type [1,2]	Statistic [3,4]	(N=xx)	(N=xx)
Monotherapy	Visit 2	Logistic MMRM	n/N (Proportion %)	xx/xx (xx.x)	xx/xx (xx.x)
			95% CI	(xx.x, xx.x)	(xx.x, xx.x)
		v. ACE-i/CCB	Odds Ratio	x.xx	
			95% CI	(x.xx, x.xx)	
			p-value	x.xxx	
Combined Therapy	Visit 3	Logistic MMRM	n/N (Proportion %)	xx/xx (xx.x)	xx/xx (xx.x)
			95% CI	(xx.x, xx.x)	(xx.x, xx.x)
		v. ACE-i/CCB	Odds Ratio	x.xx	
			95% CI	(x.xx, x.xx)	
			p-value	x.xxx	
	Visit 4	Logistic MMRM	n/N (Proportion %)	xx/xx (xx.x)	xx/xx (xx.x)
			95% CI	(xx.x, xx.x)	(xx.x, xx.x)
		v. ACE-i/CCB	Odds Ratio	x.xx	
			95% CI	(x.xx, x.xx)	
			p-value	x.xxx	

Note: The Monotherapy analysis (Visit 2) is performed on the Full Analysis Set. The Combined Therapy analysis (Visits 3 and 4) are performed on the Efficacy Population. [1] Logistic MMRM = Logistic Mixed Model Repeated Measures.

[2] A separate model is used for the monotherapy and combined therapy analyses. Models use an unstructured covariance matrix; achieving sitting BP goal as the response variable; visit, treatment subgroup, visit\*treatment subgroup interaction, and screening (monotherapy) or baseline (combined therapy) SBP/DBP as covariates; and a random effect for patient.

[3] A patient is considered to have met the Blood Pressure (BP) goal (controlled BP) if their SBP  $\leq$  130 mmHg AND their DBP  $\leq$  80 mmHg.

[4] n = number of patients who have achieved sitting BP goal at that visit. N = number of patients with data at that visit, regardless of BP goal status.

[5] ZOF/AML subgroup: Patients who were on ZOF 30 mg or AML 5 mg at Visit 1 (Week -4) and continued on same therapies.

[6] ACE-i/CCB subgroup: Patients who switched to ZOF 30 mg or AML 5 mg from any other ACE-I or CCBs at Visit 1 (Week -4).

Source: Listing 16.2.6

Program Name: XXXX.SAS

Programming Note:

• If a different covariance structure is used in case of model nonconvergence, footnote 2 should be updated accordingly.

#### Table 14.2.4.4.1 Proportion of Patients Achieving Sitting BP Goal (≤ 130/80 mmHg) at Visits 2, 3, and 4 by Hypertension Grade and Treatment Subgroup (Full Analysis Set and Efficacy Population)

				Hypertension Grade 1		Hyperten	sion Grade 2
					(N=xx)	(N	l=xx)
				ZOF/AML [5]	ACE-i/CCB [6]	ZOF/AML [5]	ACE-i/CCB [6]
Therapy Type	Visit	Statistic Type [1,2]	Statistic [3,4]	(N=xx)	(N=xx)	(N=xx)	(N=xx)
Monotherapy	Visit 2	Logistic MMRM	n/N (Proportion %)	xx/xx (xx.x)	xx/xx (xx.x)	xx/xx (xx.x)	xx/xx (xx.x)
			95% CI	(xx.x, xx.x)	(xx.x, xx.x)	(xx.x, xx.x)	(xx.x, xx.x)
			Odds Ratio	x.xx		x.xx	
		v. ACE-i/CCB	95% CI	(x.xx, x.xx)		(x.xx, x.xx)	
			p-value	x.xxx		x.xxx	
Combined Therapy	Visit 3	Logistic MMRM	n/N (Proportion %)	xx/xx (xx.x)	xx/xx (xx.x)	xx/xx (xx.x)	xx/xx (xx.x)
			95% CI	(xx.x, xx.x)	(xx.x, xx.x)	(xx.x, xx.x)	(xx.x, xx.x)
			Odds Ratio	x.xx		x.xx	
		v. ACE-i/CCB	95% CI	(x.xx, x.xx)		(x.xx, x.xx)	
			p-value	x.xxx		x.xxx	
	Visit 4	Logistic MMRM	n/N (Proportion %)	xx/xx (xx.x)	xx/xx (xx.x)	xx/xx (xx.x)	xx/xx (xx.x)
			95% CI	(xx.x, xx.x)	(xx.x, xx.x)	(xx.x, xx.x)	(xx.x, xx.x)
		v. ACE-i/CCB	Odds Ratio	x.xx		x.xx	
			95% CI	(x.xx, x.xx)		(x.xx, x.xx)	
			p-value	x.xxx		x.xxx	

Note: The Monotherapy analysis (Visit 2) is performed on the Full Analysis Set. The Combined Therapy analysis (Visits 3 and 4) are performed on the Efficacy Population. [1] Logistic MMRM = Logistic Mixed Model Repeated Measures.

[2] A separate model is used for the monotherapy and combined therapy analyses. Models use an unstructured covariance matrix; achieving sitting BP goal as the response variable; visit, treatment subgroup, visit\*treatment subgroup interaction, and screening (monotherapy) or baseline (combined therapy) SBP/DBP as covariates; and a random effect for patient. Analysis will be stratified by Hypertension grade reported at Baseline.

[3] A patient is considered to have met the Blood Pressure (BP) goal (controlled BP) if their SBP < 130 mmHg AND their DBP < 80 mmHg.

[4] n is the number of patients who have achieved sitting BP goal at that visit. N is the number of patients with data at that visit, regardless of BP goal status.

[5] ZOF/AML subgroup: Patients who were on ZOF 30 mg or AML 5 mg at Visit 1 (Week -4) and continued on same therapies.

[6] ACE-i/CCB subgroup: Patients who switched to ZOF 30 mg or AML 5 mg from any other ACE-I or CCBs at Visit 1 (Week -4).

Source: Listing 16.2.6

Program Name: XXXX.SAS

Programming Note:

# Statistical Analysis Plan

- If a different covariance structure is used in case of model nonconvergence, footnote 2 should be updated accordingly. Same applies to the table listed below.
- Repeat for the following tables:
  - 14.2.4.4.2 Proportion of Patients Achieving Sitting BP Goal (≤ 130/80 mmHg) at Visits 2, 3, and 4 by Presence of Diabetes and/or Hypercholesterolemia and Treatment Subgroup – Full Analysis Set and Efficacy Population
    - In the column headers, "Hypertension Grade 1" and "Hypertension Grade 2" will change to "Diabetes/Hypercholesterolemia Present" and "Diabetes/Hypercholesterolemia Absent", respectively.
    - Footnotes will be as follows:
      - Note: The Monotherapy analysis (Visit 2) is performed on the Full Analysis Set. The Combined Therapy analysis (Visits 3 and 4) are performed on the Efficacy Population.
      - [1] Logistic MMRM = Logistic Mixed Model Repeated Measures.
      - [2] A separate model is used for the monotherapy and combined therapy analyses. Models use an unstructured covariance matrix; achieving sitting BP goal as the response variable; visit, treatment subgroup, visit\*treatment subgroup interaction, and screening (monotherapy) or baseline (combined therapy) SBP/DBP as covariates; and a random effect for patient. Analysis will be stratified by presence of Diabetes and/or Hypercholesterolemia reported at Baseline.
      - [3] A patient is considered to have met the Blood Pressure (BP) goal (controlled BP) if their SBP ≤ 130 mmHg AND their DBP ≤ 80 mmHg.
      - [4] n is the number of patients who have achieved sitting BP goal at that visit. N is the number of patients with data at that visit, regardless of BP goal status.
      - [5] ZOF/AML subgroup: Patients who were on ZOF 30 mg or AML 5 mg at Visit 1 (Week -4) and continued on same therapies.
      - [6] ACE-i/CCB subgroup: Patients who switched to ZOF 30 mg or AML 5 mg from any other ACE-I or CCBs at Visit 1 (Week -4).

## 2.1.3 Safety

Table 14.3.1.1.1
Overall Summary of Treatment Emergent Adverse Events - Monotherapy Period
(Safety Population)

		ZOF 30 mg	AML 5 mg	All Patients
Adverse Events [1,2,3,4]	Statistic	(N=xx)	(N=xx)	(N=xx)
Total Number of TEAEs	n	xx	xx	xx
Total Number of TESAEs	n	xx	xx	xx
Total Number of ADRs	n	XX	XX	хх
Number of Patients with:				
At Least One TEAE	n (%)	xx (xx.x)	xx (xx.x)	xx (xx.x)
At Least One Severe TEAE	n (%)	xx (xx.x)	xx (xx.x)	xx (xx.x)
At Least One ADR	n (%)	xx (xx.x)	xx (xx.x)	xx (xx.x)
At Least One TEAE Leading to Study Discontinuation	n (%)	xx (xx.x)	xx (xx.x)	xx (xx.x)
At Least One TESAE	n (%)	xx (xx.x)	xx (xx.x)	xx (xx.x)
At Least One Serious ADR	n (%)	xx (xx.x)	xx (xx.x)	xx (xx.x)
At Least One TESAE with Outcome of Death	n (%)	xx (xx.x)	xx (xx.x)	xx (xx.x)

[1] AE: Adverse Event. Defined as any untoward medical occurrence in a clinical trial patient administered a medicinal product and which does not necessarily have a causal relationship with this treatment.

[2] TEAE: Treatment Emergent Adverse Event. Defined as AEs that occur after the first dose of monotherapy of ZOF or AML.

[3] TESAE: Treatment Emergent Serious Adverse Event.

[4] ADR: Adverse Drug Reaction. Defined as AEs that have a relationship of "certain," "probable," "possible," or "unassessable."

Source: Listings 16.2.7.1, 16.2.7.2, 16.2.7.3

Program Name: XXXX.SAS

Date: DDMMMYYYY

Programming Note:

• For the combined therapy period table presented in the list below: Patients will be classified as either ZOF/AML 30/5 mg or ZOF/AML 30/10 mg such that no patients are counted in both groups. That is, even though patients in the ZOF/AML 30/10 mg group are also exposed to the ZOF/AML 30/5 mg treatment, they will only be included in the ZOF/AML 30/10 mg and All Patients columns, not within the ZOF/AML 30/5 mg column. Patients that do not belong to the ZOF/AML 30/5 mg or ZOF/AML 30/10 mg group will be included only in the All Patients column.

• Repeat for the following tables:

- 0 14.3.1.1.2 Overall Summary of Treatment Emergent Adverse Events Combined Therapy Period Safety Population
  - In the column headers, "ZOF 30 mg" and "AML 5mg" will change to "ZOF/AML 30/5 mg" and "ZOF/AML 30/10 mg", respectively.

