6 SELECTION OF SUBJECTS

The following subject will be screened:

- Male or female, (Grade 1-2), uncontrolled hypertensive patients ≥18 and ≤65 years of age
- Considering a screening failure and a drop-out rate of 25%, the overall number of patients to be screened is 290.
- 216 patients needed to complete the run-in period and enter the assessment period to guarantee powered results

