### 4 Study Methods

### 4.1 General Study Design and Plan

This is a phase IV, open-label, multicenter, multinational study with 2 study periods: a 4-week run-in period and an 8-week assessment period.

Approximately 290 patients are planned to be screened to ensure at least 216 patients complete the run-in period and start with the assessment period.

Patients with Grade 1-2 hypertensive patients (blood pressure [BP] ranging from  $\geq$ 140/90 mmHg to  $\leq$ 179/109 mmHg) on treatment with any angiotensin converting enzyme inhibitors (ACE-i) including Zofenopril 30 mg or with calcium channel blockers (CCBs) including Amlodipine 5 mg will be screened for eligibility (Visit 1).

Allowed CCBs: Felodipine, isradipine, lacidipine, lercanidipine, nicardipine, nifedipine, and nisoldipine. Patients treated with other dosages of Zofenopril (other than 30 mg) are not allowed to be screened.

After screening, on the same day, eligible patients, will enter into a 4-week run-in period, during which patients on other ACE-i will be assigned to monotherapy with ZOF 30 mg while patients on CCBs will be assigned to monotherapy with AML 5 mg for 4 weeks. Patients with on-going treatment zofenopril 30 mg and amlodipine 5mg will continue on the same treatment for 4 weeks.

After the run-in period (4 weeks  $\pm$  2 days), BP will be further assessed (Visit 2), if BP levels are over the defined controlled target goal (sitting SBP/DBP >130/80 mmHg), treatment is well tolerated and adherence to the treatments ranges from 80% to 120%, patients will enter the assessment period, where they will be assigned to the extemporaneous combination of ZOF 30 mg and AML 5 mg. At Visit 2 patients with SBP/DBP values classified as Grade 3 (SBP  $\geq$  180 or DBP  $\geq$  110 mmHg) hypertension will be withdrawn from the study.

If patients, at Visit 2, after the run-in period, have a controlled BP (sitting SBP/DBP≤130/80 mmHg) or do not tolerate the treatment or have an adherence range below 80% or superior to 120%, they will be withdrawn from the study.

The patients will be assessed for further 8 weeks (assessment period).

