### 5.2 Study Variables

### 5.2.1 Baseline

Patients are instructed to take the study treatment after all visit evaluations have been performed on scheduled visit days. Assessments performed at Visit 2 will be considered Baseline since the first dose combination therapy (ZOF/AML) occurs after the completion of Visit 2 assessments. For assessments performed at Visit 1 and not Visit 2 (e.g., laboratory and ECG assessments), the Visit 1 assessment will be considered Baseline.

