### 5.3.2 Safety Population (SAF)

The Safety Population (SAF) is defined as all study participants in the Full Analysis Set who meet all screening criteria, are enrolled, and receive at least one dose of the assigned treatment during the runin period. This population will be used for safety analyses.

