### 5.5 Reporting Conventions

The following conventions will be used across all study summaries and analyses, unless otherwise specified in the corresponding section.

- Summary statistics will consist of sample size (n), mean, standard deviation (SD), median, minimum (min), and maximum (max) values for continuous and some ordinal variables; and sample size (n), frequencies, and percentages (%) for categorical and some ordinal variables.
- Statistical tests and confidence intervals (CI) will be two-sided unless otherwise specified; statistical tests will use an alpha threshold of 0.05 and CIs will use 95% confidence unless otherwise specified.
- Mixed Models for Repeated Measures (MMRM) will be fit using the unstructured covariance matrices. In the event of lack of model convergence, other covariance structures may be used.
- P-values will be calculated to three decimal places. P-values less than 0.001 will be presented as "< 0.001."

Unless otherwise specified, descriptive summary tables will be structured with a column for each monotherapy group (ZOF 30 mg or AML 5 mg) or combined treatment group (ZOF/AML 30/5 mg or ZOF/AML 30/10 mg) and overall (All Patients) and will include the total population size for each group in the header. Conversely, inferential summary tables will use only the All Patients column, unless otherwise specified, to prevent overinflation of the type I error rate.

For descriptive summary tables, patients will be classified as either ZOF/AML 30/5 mg or ZOF/AML 30/10 mg such that no patients are counted in both groups. That is, even though patients in the ZOF/AML 30/10 mg group are also exposed to the ZOF/AML 30/5 mg treatment, they will only be included in the ZOF/AML 30/10 mg and All Patients columns within the summary tables, and not within the ZOF/AML 30/5 mg column.

Summary tables will also indicate the number of patients with complete data for each measurement, event, or outcome.

Data listings will be sorted by treatment group, patient, and visit (when applicable).

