- When summarizing severity of the AEs (mild, moderate, severe), if there are multiple AEs of the same preferred term but different severity during an analysis period for a patient, the AE with the maximum severity will be reported. If the AE term (SOC and PT) is reported more than once, one of them with missing severity, and at least another with non-missing severity, the maximum severity will be chosen from the non-missing severity and the missing severity can be ignored. If all are of missing severity, then the AE severity will be summarized with an additional "Missing" category. In summary of severe AEs, missing severity will be included in severe category following the conservative approach.

All AE tabulations for the monotherapy period will present the incidences separately for the monotherapy groups (ZOF 30 mg or AML 5 mg) and All Patients for the SAF population. That is, all patients who experienced at least one AE in the monotherapy period will be summarized together in the All Patients column of the corresponding summary tables. All patients who take ZOF 30 mg will be summarized in the ZOF 30 mg column and all patients who take AML 5 mg will be summarized in the AML 5 mg column.

All AE tabulations for the combined therapy period will present the incidences separately for the combined treatment groups (ZOF/AML 30/5 mg or ZOF/AML 30/10 mg) and All Patients for the SAF population. That is, all patients who experienced at least one AE in the combined therapy period will be summarized together in the All Patients column of the corresponding summary tables. All patients who take ZOF/AML 30/10 mg will be summarized in the ZOF/AML 30/10 mg column, even for AEs that occurred while taking the ZOF/AML 30/5 regimen. Lastly, all patients who take ZOF/AML 30/5 mg for the duration of the combined therapy period will be summarized in the ZOF/AML 5 mg column.

In summaries by SOC and PT (for both monotherapy and combined therapy periods), AEs will be sorted by descending frequency for SOC and PT in the All Patients column. All AEs will also be presented in bypatient data listings for Adverse Events for the SAF population.

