## 2 Mock TLF Shells

## Tables

### 2.1.1 Demographic Data

		ZOF/AML 30/5 mg	ZOF/AML 30/10 mg	All Patients
Disposition [1,2,3]	Statistic	(N=xx)	(N=xx)	(N=xx)
Total Number of Patients				
Screened	n			XX
Screen Failures	n (%)			xx (xx.x)
Enrolled	n	xx	xx	xx
Completed Monotherapy	n (%)	xx (xx.x)	xx (xx.x)	xx (xx.x)
Completed Combined Therapy	n (%)	xx (xx.x)	xx (xx.x)	xx (xx.x)
Completed the Study	n (%)	xx (xx.x)	xx (xx.x)	xx (xx.x)
Discontinued the Study	n (%)	xx (xx.x)	xx (xx.x)	xx (xx.x)
Reason for Study Discontinuation				
Excluded at Visit 2	n (%)	xx (xx.x)		xx (xx.x)
Excluded at Visit 3	n (%)	xx (xx.x)		xx (xx.x)
Meets Exclusion Criteria	n (%)	xx (xx.x)	xx (xx.x)	xx (xx.x)
Adverse Event	n (%)	xx (xx.x)	xx (xx.x)	xx (xx.x)
Study Non-Compliance	n (%)	xx (xx.x)	xx (xx.x)	xx (xx.x)
Withdrawal of Consent	n (%)	xx (xx.x)	xx (xx.x)	xx (xx.x)
Failure to Report to Study Visits	n (%)	xx (xx.x)	xx (xx.x)	xx (xx.x)
Lost to Follow-up	n (%)	xx (xx.x)	xx (xx.x)	xx (xx.x)
Investigator Decision	n (%)	xx (xx.x)	xx (xx.x)	xx (xx.x)
Lack of Efficacy	n (%)	xx (xx.x)	xx (xx.x)	xx (xx.x)
Pregnancy	n (%)	xx (xx.x)	xx (xx.x)	xx (xx.x)
Protocol Deviation	n (%)	xx (xx.x)	xx (xx.x)	xx (xx.x)
Study Terminated by Sponsor	n (%)	xx (xx.x)	xx (xx.x)	xx (xx.x)
Abnormal Renal Function or Liver Enzyme	n (%)	xx (xx.x)	xx (xx.x)	xx (xx.x)
Death	n (%)	xx (xx.x)	xx (xx.x)	xx (xx.x)
COVID-19	n (%)	xx (xx.x)	xx (xx.x)	xx (xx.x)
Other	n (%)	xx (xx.x)	xx (xx.x)	xx (xx.x)

Table 14.1.1 Patient Enrollment and Disposition (Full Analysis Set)

[1] Percentages for Screen Failures is based on the number Screened. Percentages for all subsequent percentages are based on the number Enrolled.

[2] Excluded at Visit 2 = Patients with controlled BP, patients who do not tolerate the treatment, or patients < 80% or > 120% treatment adherence.

[3] Excluded at Visit 3 = Patients who do not tolerate the extemporaneous combination of treatment, or patients < 80% or > 120% treatment adherence.

Source: Listing 16.2.1 Program Name: XXXX.SAS

Date: DDMMMYYYY

Programming Note:

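### The overall combination-period adverse event percentage appears to include run-in patients who never took the combination, and AE start-date imputation uses an anchor date those patients do not have

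*SAP*

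**What the plan says.** **Population.** SAP 5.3.2 admits a screened and enrolled patient to the Safety Population if they "receive at least one dose of the assigned treatment during the runin period". All AE tables, for both periods, use this population.

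**Withdrawal at Visit 2.** SAP 4.1 removes patients with controlled or Grade 3 blood pressure at Visit 2. Those who "do not tolerate the treatment or have an adherence range below 80% or superior to 120%, they will be withdrawn from the study" as well. SAP 5.2.1 says that "the first dose combination therapy (ZOF/AML) occurs after the completion of Visit 2 assessments", so these patients get no combination dose.

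**All Patients column.** The TLF shells (section 2.1.3, notes under Tables 14.3.1.1.1 and 14.3.1.2.1) say of the combined-period AE tables: "Patients that do not belong to the ZOF/AML 30/5 mg or ZOF/AML 30/10 mg group will be included only in the All Patients column". SAP 5.5 says that descriptive tables "will include the total population size for each group in the header". SAP 8.2 adds that "all patients who experienced at least one AE in the combined therapy period will be summarized together in the All Patients column". That describes who contributes an event and sets no exposed-only denominator. Table 14.1.1, by contrast, does state its base: "Percentages for all subsequent percentages are based on the number Enrolled".

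**Dose columns.** SAP 8.2 puts up-titrated patients in the 30/10 column. The 30/5 column is for patients who stay on 30/5 throughout the combined period.

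**Dates.** SAP 5.2.2 defines first dose as the first combination dose and excludes monotherapy. SAP 5.6.2 imputes incomplete AE start dates from that first dose, with the stated aim of deciding treatment emergence. SAP 8.2 counts AEs as treatment-emergent from the first monotherapy dose and splits the periods at the day of Visit 2. Listing 16.2.7.1 gives every AE a period, monotherapy or combined.

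**The concern.** Safety of the combination is part of secondary Endpoint 2.5, and the All Patients column is the only place where its overall AE percentage appears. If people who never took the combination are in the denominator, that percentage mixes exposed and unexposed patients. It comes out too low whenever the unexposed have fewer AEs on the day of Visit 2 than the exposed have over eight weeks. For a safety summary this is the unfavourable direction.

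The date rule raises a separate issue. A rule meant to identify events after the first monotherapy dose is tied to a later dose that some Safety Population members never receive. For them it cannot be carried out. For the others, it could move an incompletely dated run-in event into the combination period if the imputed date is also used to assign the period.

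**Working it through.** **1. The plan's own numbers.** SAP 4.1 plans about 290 screened so that at least 216 start the assessment period. With the stated 25% allowance, 216/0.75 = 288, close to 290. Protocol 6 says: "Considering a screening failure and a drop-out rate of 25%, the overall number of patients to be screened is 290". The 290 therefore includes screening failures, who are not in the Safety Population. Protocol 12.2 and SAP 4.6 call the same 290 enrolled, so the documents do not fix the Safety Population size.

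**2. Which tables.** The note covers 14.3.1.1.2, 14.3.1.2.2, 14.3.1.3.2, 14.3.1.4.2, 14.3.1.5.2, 14.3.2.1.2, 14.3.2.2.2 and 14.3.2.3.2: eight tables. The sentence is absent from the combined-period vital-sign and physical-examination shells and from the laboratory shells, so the shells are not uniform.

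**3. Dilution.** Let E be the exposed N, S the Safety Population N, r the AE rate in exposed patients, and q the share of never-exposed patients with an AE on the day of Visit 2. Such an AE falls in the combination window of SAP 8.2.

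Shown rate = (E·r + (S − E)·q)/S. With q = 0 the factor is E/S.

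E = 216 is the planned minimum. S, r and q are assumptions.

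- S = 216: 216/216 = 1.00
- S = 240 (24 never exposed): 216/240 = 0.90
- S = 260 (44 never exposed): 216/260 = 0.83
- S = 290 (74 never exposed): 216/290 = 0.745, which would need every screened patient to be dosed

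For r = 20%, E·r = 43.2:

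- S = 240: 43.2/240 = 18.0% with q = 0; (43.2 + 24 × 0.10)/240 = 19.0% with q = 10%
- S = 260: 43.2/260 = 16.6%; (43.2 + 44 × 0.10)/260 = 18.3%
- S = 290 (limit): 43.2/290 = 14.9%; (43.2 + 74 × 0.10)/290 = 17.4%

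Protocol 5.1 caps Visit 2 entry at 110 per monotherapy, so E could reach 220. The factors are then 220/240 = 0.92 and 220/260 = 0.85.

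**4. Do the dose columns add up to E?** SAP 5.5 classifies patients as either 30/5 or 30/10. SAP 8.2 defines the 30/5 column by use over the whole combined period. A patient who takes 30/5 and stops at or before Visit 3 meets neither definition in 8.2 and may appear only in All Patients. In the Table 14.1.1 shell, the 30/5 column has an entry for patients excluded at Visit 3, and also one for patients excluded at Visit 2, who had no combination dose. Column membership is therefore not settled.

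**5. Does a run-in AE lose its flag?** Under SAP 5.6.2 a true run-in onset is set to one of three dates: the combination dose date, the last day of the onset month, or 31 December of the onset year. None is earlier than the true onset, so the event stays treatment-emergent. A patient without a combination dose has no anchor date.

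**6. Period shift, only if the imputed date also sets the period.** Assume a 28-day run-in with onsets spread evenly, over 365 possible Visit 2 dates: 365 × 28 = 10,220 onsets.

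- Start date fully missing: all are set to the combination dose date, 100%
- Month missing: same year as Visit 2 in 9,814; 9,814/10,220 = 96.0%
- Day missing: same month and year as Visit 2 in 5,348; 5,348/10,220 = 52.3% (55.6% for 26 days, 49.1% for 30 days)

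**7. Would re-anchoring alone cure it?** No. If everything is anchored to the first monotherapy dose, true combination onsets in the eight weeks after Visit 2 move into the run-in: 100% of those fully missing, about 92% with month missing and about 26% with day missing.

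**The case against.** The strongest reply is that the denominator is inferred. SAP 5.5 requires a population size in the header and does not say that AE percentages are divided by it. This stands: the dilution is the natural reading, not a stated rule. The absence of a denominator footnote is itself worth correcting.

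Second, the effect is limited and partly visible. The column is labelled All Patients, the dose columns carry the combination-specific results, and no hypothesis test is involved. Table 14.3.5 prints the number dispensed each drug at Visit 2, and Table 14.1.1 counts exclusions at Visit 2, so a careful reader could approximate the exposed-only rate. This also stands and limits the severity. It does not justify leaving the headline figure for the reader to repair.

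Third, SAP 8.2 already fixes a day-level convention at Visit 2, and the AE listing shows no onset time. That is fair for exposed patients. Only an AE on that day in a patient who gets no combination dose is misplaced. Nothing in the documents supports a value of q as high as 10%; it is shown only to bound the result.

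Fourth, SAP 5.6.2 gives treatment emergence as its purpose and does not mention the period. The shares in step 6 therefore depend on an unstated use of the imputed date, and they are shares of a probably small number of incompletely dated AEs.

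**Conclusion.** The point holds at minor to moderate weight. Followed as written, the combined-period AE tables keep never-exposed run-in patients in the All Patients column. If the header N is the denominator, the overall combination AE percentage is diluted by a factor of about 0.90 to 0.83 for a Safety Population of 240 to 260 with 216 exposed. These population sizes are assumed.

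A reader might infer more than this, and four readings should be avoided:

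- That the loss is a quarter. The 0.745 figure needs all 290 screened patients to be dosed, and the 290 allows for screening failures.
- That never-exposed patients dilute the dose columns. The AE table notes put patients in neither group in All Patients only. The opposite claim, that the dose columns are complete and sum to the exposed N, is not established either, because of the 30/5 definition in SAP 8.2.
- That run-in AEs lose their treatment-emergent flag. They do not. The defect is a missing anchor for patients who never took the combination.
- That half or more of run-in AEs are moved to the combination period. This can concern only incompletely dated AEs, and only if the imputed date also assigns the period.

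The note for monotherapy Table 14.3.1.4.1 sets 30/5 and 30/10 column headers. That is a clerical slip, since SAP 8.2 already specifies ZOF 30 mg and AML 5 mg columns for that period. The primary efficacy analysis is not affected.

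**What to change.** - **Denominator.** Base the eight combined-period AE tables on Safety Population patients with at least one combination dose, and footnote that denominator. State a rule that places every exposed patient, including early stoppers, in one dose column.
- **Day of Visit 2.** Assign an AE on that day to the monotherapy period if the patient received no combination dose. Keep the day convention of SAP 8.2 for exposed patients.
- **Dates.** Use the first monotherapy dose as the anchor for the treatment-emergent flag only. Assign the period of an incompletely dated AE by a separate rule from the known date parts and the end date, and report how many remain undetermined. Do not simply re-anchor all imputation (step 7).
- **Header.** Align Table 14.3.1.4.1 with SAP 8.2.

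The cost is wording in the SAP and shells. No new table or data are needed: AE start and end dates are planned for Listing 16.2.7.1, and dosing dates and times for Listing 16.2.5.2. The All Patients N will differ between the monotherapy and combination tables and must be labelled, and some AEs may stay without an assigned period.
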